We propose a patient-centered and community-focused management program (IMPACT-AF) to grasp these opportunities and determine if patients with AF can be managed as effectively (clinical outcomes) and more efficiently (economic outcomes) in primary care as they are in specialized care. The premise of IMPACT-AF is that primary care providers within the community when supported by an electronic AF patient management system that offers: a) clinical decision aids based on clinical guidelines for AF; and, b) a communication medium for data sharing and referrals, with the specialized AF management centre in Halifax, will lead to improved diagnosis and standardized disease management, including increased use of proven therapies for AF rhythm and rate management, and better stroke prevention. We expect - frequent measurement and feedback of actual care practices, patient outcomes and other relevant disease / health information, to drive positive behaviour in both practitioners and patients. The overall result will be cost-efficient improvement of care and outcomes for AF patients.

The primary outcome is a decrease in CV hospitalizations, with secondary outcomes of clinical, process of care and economic relevance. The cluster-randomized study design will permit measurement and comparison of the clinical decision support system pre and post intervention, and across cases. A principal assumption is that IMPACT-AF will build on the principles and practices of benchmark disease management projects like ICONS, particularly in aligning with provincial and regional health policies that direct support to primary care and data management resources that address public health burdens. We anticipate that IMPACT-AF will successfully extend a more clinically effective, cost-efficient and sustainable social-networking model of health management to a segment of our aging population who need things to be better. In doing so, IMPACT-AF will also produce, markedly improved stakeholder outcomes and satisfaction – all of which can be modeled in other areas of health care priority.

Table of Contents

List of Abbreviations 5

1.0 BACKGROUND AND RATIONALE 6

 1.1 The Problem: Increasing Burden, Significant Risk and Care Gaps 6

 1.2 Relevant New Knowledge 9

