3.4 Intervention Arm

Participating practices in the intervention arm will receive access to the clinical decision support system (CDSS) intervention in their primary care setting. The CDSS is an integrated management system that involves many facets of the healthcare system. It will focus on four key elements:

- 1) Translation of best-evidence to Primary Care Providers (PCP) through computerized decision support aids designed to enable PCP to handle the identification and rapid treatment of AF patients at the primary care level;
- 2) Engagement and empowerment of patients in the self-management of their disease;
- 3) Remote surveillance of AF patients through a range of data streams with proactive response to critical trends and situations;
- 4) Leveraging innovative health informatics and computer science technologies to develop an integrated knowledge-centric patient-centered disease management platform (DMP).

Interventions most frequently cited as efficacious to improve care and outcomes in disease management include: stakeholder education and reminders of best care practices; financial incentives to follow best practices; and, regular measurement and feedback of actual practices and outcomes [101]. In the successful ICONS project, financial incentives were not used; instead, a combination of education, reminders and repeated measurement and feedback communication of practices and outcomes were all employed, including the sharing of region-specific and sub-group data [103-106].

Figure 5. Study Flow Diagram

CONFIDENTIAL

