3.6 Sources of Bias

In cluster-randomized trials, there are important sources of bias to consider: recruitment bias, baseline imbalance and loss of clusters [122]. Recruitment bias should be limited as all patients in each PCP practice will be included, thereby minimizing bias in types of AF patients. Baseline imbalance is unlikely to be an issue as there are a large number of clusters in this study. Loss of clusters is possible but unlikely since there is little migration of PCPs from Nova Scotia; thus, loss of an entire cluster over the period of follow-up is improbable.

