3.7 Study Procedures

3.7.1 Randomization

Primary care centres will obtain their randomized assignment (intervention versus control) at the time of recruitment. (See Section 4.0 for Study Recruitment Procedures.) Randomization will be stratified by whether the PCP is urban or rural. Urban is defined as a population $\geq 10,000$, while rural is defined as $< 10,000$ population [123].

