3.7.3 Data Collection

Once informed consent has been obtained by the patient's PCP, a process to record retrospective baseline and ongoing clinical data prospectively will be implemented. Patients will be also requested to complete a patient case report form and quality of life questionnaire (either paper-based or electronic format) to gather relevant demographic and socioeconomic data.

Acknowledging the age profile of AF patients in NS, it is anticipated that a proportion of

CONFIDENTIAL

participants will chose not to complete online surveys or interact with the web-based tool. Completion of the web-based survey tools and / or interacting with the web-based tool, the AF Care Partner, is not mandatory for participation; all survey tools will be available to participants in a paper-based format.

In both study arms, baseline clinical data will be captured from the patient's chart by a data abstractor via on-site visit(s). Abstractors will utilize a laptop computer or tablet to record and transmit study data to secure and password protected servers located behind a firewall at Health Information Technology Services Nova Scotia (HITS-NS). This process will be repeated at 12 months for follow-up data collection in both study arms. Follow-up data for the intervention arm will also be captured through examination of data gathered during use of the CDSS.

The majority of patients at the start of the study are expected to have a past diagnosis of AF. As the study progresses, newly diagnosed patients are anticipated to be enrolled.

Review of PCP records will be done at 12 months to ensure completeness of outcome events. Clinical event / outcomes data will also be captured via review of hospitalization records for consented patients. Patients visiting the AF clinic in Halifax will be consented and data captured during their clinic visit. See Section 4.2 for further details.

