Information to be collected on all patients will include contact details, demographic and socioeconomic characteristics, and, clinical, process of care and health outcome variables such as: Name, year and month of birth, health card number, mobile phone number, mailing address, internet access / smart-phone and social media usage, type of residence, gender, ethnicity, date of AF diagnosis, means of documentation of AF (ECG, Holter, other), medications, risk factors for AF, bleeding and stroke (based on HASBLED, CHADS2 and / or CHA2DS2-Vasc score), prior cardiovascular or other hospitalizations and ER / AF clinic / GP office visits for AF care, laboratory investigations (e.g., thyroid studies, renal function, hemoglobin, INR), referrals, alcohol use, smoking status, cardiac risk factors, other co-morbidities / past interventions and information on the patient's pharmacies of choice. Additional information that will be sought will relate to socioeconomic, quality of life and satisfaction with care (e.g., marital / employment status, annual household income, education level, care giver support, missed work, EQ-5D-5L questionnaire). See supporting data collection materials for a complete list of variables that will be captured from the patient and or the provider via Case Report / Data Collection Forms.

Table 2. Overview of variables collected during the study

Schedule Procedure	Initial Primary Care / AF Clinic Visit	Follow-up Visits	Tertiary Care (if applicable)
Visit date	X	X	X
Demographic data	X		
Medical history	X		
Investigations / Labs / Vital signs	X	X	X
Medications / Interventions	X	X	X
Socioeconomic / HRQoL	X	X	

CONFIDENTIAL

Events (including details)	X	X	X
----------------------------	---	---	---

Costs

The relevant costs for this study may include the cost associated with the development, implementation, and maintenance of the CDSS. All the health care resource utilization associated with managing and treating participating patients with AF will also be recorded. This health care resource utilization may occur in the participating primary care providers and the tertiary AF care clinic.

HRQoL

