4.0 Study Population

4.1 Recruitment of Clinics and Practitioners Managing AF Patients

IMPACT-AF will seek participation from a wide variety of primary care providers managing AF patients within Nova Scotia. All patients with a prior or new electrocardiographically confirmed diagnosis of AF during the study period will be eligible for inclusion as part of the study.

Inclusion Criteria: Any licensed medical provider of community-based adult patients with a minimum of 15 diagnosed AF patients enrolled in the study from their practice will be eligible to participate. To avoid bias based on technological availability or proficiency, all eligible providers are required to have access to high-speed internet access in their office for the duration of this study. As well, participating providers must sign a site agreement which outline the following terms:

- Agree to participate for the duration of the study;
- Notify the research team if your practice:
 - Is located in an urban (population $\geq 10,000$) or rural (population $< 10,000$) setting; and,
 - Operates as a collaborative practice (i.e., shares in the care of patients with at least one other health care provider);
- Attend and participate in investigator meetings;
- Identify all eligible patients in your practice who meet the study inclusion criteria;
- Invite all eligible participants to join in the study (either in person or via mail outs);
- Perform informed consent discussions with eligible participants who visit your practice for routine care;
- Accept randomization into either the control or intervention group;
- Agree to store informed consent forms and completed patient questionnaires in locked filing cabinets in an access-controlled location within your practice (after faxing a copy to the study office);
- Agree to be trained on and use the web-based decision support tool, if assigned to the intervention group;
- Allow the study team access to medical records for consented study participants at baseline and follow-up;
- Facilitate the distribution of patient questionnaires (all materials supplied by the research team);

CONFIDENTIAL

- Notify the Privacy Officer at HITS-NS that the study team is to be granted access to data for all patients who consent to study inclusion and provide copies of patient signed consent forms as requested.
- Report any problems that you experience related to your participation in the study.

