Once eligible patients are identified, a consent brochure will be mailed or handed to the patient. If the patient is seen in the provider's office, consent will be sought at the time of visit. Each patient will be assigned a study number for coding purposes; otherwise, unique identifiers for health record identification and linkage will remain with the health facility at which they were recruited and where their AF care is routinely provided. This affords a mechanism to allow follow-up on long-term care procedure and events through subsequent chart review or database linkage without having to include unique health identifiers in the IMPACT-AF study registry.

AF Clinic ID / Recruitment: Patients visiting the AF Clinic at the QEII Health Science Centre will also be asked to participate and sign a consent form. The patient's primary care provider would be notified that the patient has agreed to participate via the AF clinic site.

Inclusion Criteria:

Primary Care: All new and previously diagnosed patients ≥ 18 years of age with AF and a life expectancy > 12 months will be eligible for study enrollment. In addition, patients will need to be:

- A registered and regular patient at a primary care practice participating in the IMPACT-AF study;
- Able to read, understand and communicate in English.
- A resident of Nova Scotia.

Patients in the Intervention Arm will have the option to interact with the CDSS through the patient portal, the AF Care Partner tool. These patients will therefore need access to the Internet and be willing to input information and receive feedback and reminders from the AF Care Partner tool over the duration of the study. Patients can revoke their AF Care Partner tool participation if desired.

CONFIDENTIAL

All AF Clinic (QEII HSC) patients will be invited to participate in the IMPACT-AF study by signing an informed consent form.

Exclusion Criteria: Patients with a terminal illness (expected death within 12-months) and those having cognitive impairment or who are unable to communicate in English will be considered ineligible for participation. Also ineligible for inclusion are AF patients whose care is being significantly overseen by a specialist as well as those who are patients of the hospital-based AF clinic at the QEII Health Sciences Centre.

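### Patients first diagnosed after their practice is allocated are pooled with prevalent cases, although the CDSS is meant to improve diagnosis; the case mix could differ by arm, and no planned analysis would show whether it matters.

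*Protocol*

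**What the plan says.** On timing, protocol section 3.7.1 states: "Primary care centres will obtain their randomized assignment (intervention versus control) at the time of recruitment". The trial is unblinded (section 3.1), and patients are then identified and consented by the practice (sections 3.7.3 and 4.2).

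On who may enter, section 4.1 states: "All patients with a prior or new electrocardiographically confirmed diagnosis of AF during the study period will be eligible for inclusion". Section 4.2 applies one rule to "All new and previously diagnosed patients", and section 3.7.3 expects that "As the study progresses, newly diagnosed patients are anticipated to be enrolled".

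On what the intervention is for, the protocol's opening summary expects that supported primary care "will lead to improved diagnosis and standardized disease management". Section 3.4 describes decision aids "designed to enable PCP to handle the identification and rapid treatment of AF patients at the primary care level". Only the intervention arm has the system.

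On protection against bias, section 3.6 argues that every patient in a practice will be included, "thereby minimizing bias in types of AF patients".

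On analysis, the primary model in protocol section 3.9 and in the SAP adjusts only for urban or rural practice. Section 3.9 also promises a sensitivity analysis for baseline imbalance but names no covariates. The SAP's Sensitivity Analyses section and its Table 1 do not carry that analysis forward. SAP Table 2 has a descriptive row for newly diagnosed AF. The SAP's subgroups do not include new versus prevalent AF.

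**The concern.** In a cluster trial with open allocation before enrolment, patients are comparable across arms only if the allocation does not influence who enters. Differential consent is the familiar threat. This one is separate. If the intervention changes which patients are diagnosed, it changes the pool from which patients are drawn, and complete consent in both arms would not repair that. Including every diagnosed patient is no protection when being diagnosed may itself be an effect of the intervention.

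The primary outcome is affected only if new and prevalent cases also differ in 12-month risk. The documents give no rates by case type, but they make a difference plausible in either direction. The SAP background says at least a third of AF patients have no symptoms and that many cases come to light during assessment for something else. Protocol section 1.1 says about a third attend the emergency room at some time because of symptoms. A case found by opportunistic search and one found through an acute episode need not carry the same later risk of an AF-related emergency visit or cardiovascular admission.

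At stake is whether part of an observed arm difference could be case mix, and whether a reader could tell.

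**Working it through.** **1. The plan's own figure.** Inputs from protocol section 3.8: 50% versus 40%, two-sided alpha 0.05, power 80%, ICC 0.05, 9 patients per cluster.

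- Variance inflation: 1 + (9 − 1) × 0.05 = 1.4.
- Unadjusted total, with the sum of the normal quantiles rounded to 2.8: 2 × 2.8² × (0.25 + 0.24) / 0.10² = 768.32.
- Adjusted total: 768.32 × 1.4 = 1075.65, as in Table 3 (1076.9 with unrounded quantiles).

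The stated 1075 reproduces, so the point does not depend on an error there. The calculation treats the arms as exchangeable and makes no allowance for case mix. The effective size is 537 / 1.4 = 383.6 per arm, with power 79.6%.

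**2. Spurious difference.** With no true effect, and the same risk within each case type in both arms:

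shift = (share of new cases, intervention − control) × (12-month risk, new − prevalent).

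The documents give neither factor. The values below are assumptions; either sign is possible. The last column is the chance of a significant result when there is no effect, taking a 50% base rate, 383.6 effective patients per arm and a comparison of two proportions.

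| Share gap | Risk gap | Shift | Part of 10-point target | Type I error |
|---|---|---|---|---|
| 2 points | 10 points | 0.2 points | 2% | 5.0% |
| 5 points | 20 points | 1.0 point | 10% | 5.9% |
| 10 points | 20 points | 2.0 points | 20% | 8.6% |
| 10 points | 30 points | 3.0 points | 30% | 13.2% |
| 15 points | 30 points | 4.5 points | 45% | 23.9% |

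The table uses the proportion scale of section 3.8. The SAP reports hazard or rate ratios, so it shows order of magnitude, not the bias in the SAP's estimate.

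**3. What a restricted analysis could show.** Let s be the share of patients diagnosed after randomisation, taken as equal in the arms. Each arm keeps 537 × (1 − s) patients, in clusters of 9 × (1 − s). For 50% versus 40%:

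| s | Patients per arm | Variance inflation | Power |
|---|---|---|---|
| 5% | 510 | 1.3775 | 78.2% |
| 10% | 483 | 1.355 | 76.7% |
| 20% | 430 | 1.31 | 73.1% |
| 30% | 376 | 1.265 | 68.9% |

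**4. Can the split be made?** Yes. Section 3.7.3 collects "date of AF diagnosis, means of documentation of AF", and each practice has a randomisation date. The newly diagnosed row in SAP Table 2 is not enough: it classifies AF at baseline and is not tied to that date.

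**The case against.** The strongest reply is that the mechanism is thin. The system as described in section 3.4.1 has no screening function. It works on data the physician enters for a given patient and helps manage that patient. The SAP background describes its purpose as better AF care, antithrombotic management, rate control and treatment of risk factors. Case finding is also arm-neutral on paper: section 4.2 tells all participating practices to search their entire patient population, beyond patients already known to have AF, and supplies the same search methods and staff support without distinction by arm. Section 3.7.3 expects most patients at the start to have a past diagnosis. Section 4.2 puts diagnosed patients at 20 to 30 per practice; taking 200 providers as 200 practices, that is 4,000 to 6,000 prevalent patients against 1,075 needed, so a large share of new cases is not obvious.

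All of that stands, and it sets the limit of the point. A reader might infer that the arms would differ in case mix, or that new-onset AF is known to carry a different risk. The documents support neither: the first is conditional on the system changing diagnosis in practice, and the second is an assumption.

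It can also be said that section 3.9 already foresees baseline imbalance. It does, but it names no covariates and the SAP drops it. Finally, new diagnoses are enrolled deliberately, and a trial of community AF patients should include them. That is a good reason to leave the primary analysis alone, but not to omit a check.

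**Conclusion.** The point holds in a limited form. Open allocation precedes enrolment, later diagnoses are pooled with earlier ones, and improved diagnosis is a stated aim of an intervention that one arm receives. The case mix could therefore differ by arm even with full consent, and the statement in section 3.6 does not cover cases diagnosed after randomisation.

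On the assumed ranges the effect runs from negligible (0.2 points, type I error unchanged at 5.0%) to material (4.5 points, 23.9%). The documents do not say where in that range the trial lies, or in which direction. They do not support a conclusion that the primary result is biased. The defect is that no specified analysis would distinguish a trivial imbalance from one that matters, although the diagnosis date needed is already collected. This is a worthwhile, cheap improvement, not a fault that undermines the design.

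**What to change.** - In protocol section 3.9, and in the SAP's Sensitivity Analyses section and Table 1, add a supportive, pre-specified analysis of the primary composite restricted to patients whose AF diagnosis date is on or before their practice's randomisation date. Use the same GEE model as the primary analysis, and state how a missing diagnosis date is handled.
- Report by arm the number and share of patients diagnosed after that date.
- Qualify the statement in section 3.6 so that it does not claim protection for those patients.
- Do not make the restricted analysis a condition for the primary claim. Report its estimate and confidence interval beside the primary result; it need not reach significance on its own.

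The cost is one extra model and a few lines of text, with no change to recruitment or data collection. The restricted set is less precise, with power of about 78% to 69% if 5% to 30% of patients are new cases. The primary analysis and its power are unchanged. The restricted analysis does not address differential consent after open allocation, which is a separate matter.

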3.7.4 Data Quality

A Data Quality Coordinator will monitor data quality to ensure accuracy. This will be done via random audits of case report forms. All data captured in the study database will be validated at time of entry. Missing or implausible data will be queried.

3.7.5 Safety / Adverse Events

The IMPACT-AF study is not involved with examining novel therapies, but rather innovative approaches to optimizing proven, evidenced-informed care. Study outcomes such as bleeding will be monitored as a safety outcome, but a data safety and monitoring committee is not anticipated given the study is supporting uptake of Canadian guideline-based approaches to care.

3.8 Sample Size

The primary objective of the proposed study is a composite of unplanned cardiovascular hospitalizations in AF patients and any AF-related emergency department visits. The sample size calculation is based on the test of the null hypothesis that the percentages of patients with cardiovascular hospitalizations in the two populations (CDSS and usual care) are equal. The primary measure of effect is the difference in proportions of patients with composite of any AF-related emergency department visit or unplanned CV hospitalization over 12 months. The criterion for significance (alpha) has been set at 0.05. With the proposed sample size of 1075 primary care patients (537 per intervention/control arm, assuming a 1:1 allocation ratio), the study will have power of 80% to yield a statistically significant absolute difference of 10% (or 20 [RRR] relative risk reduction) between the two percentages of patients with composite of any AF-related emergency department visit or unplanned CV hospitalization in the control and intervention groups, assuming 50% annual rate of CVD hospitalizations for the control group. This sample size was adjusted for a potential clustering of patient outcomes within a physician, by assuming an intra-physician correlation coefficient (ICC) of 0.05 with an average cluster size of 9 patients/physician. The ICC is based on studies done in the primary care sector reporting this magnitude of ICC. This extent of reduction was felt to represent a minimal clinically important achievement by a consensus of study investigators and has been an endpoint target in other studies in AF populations of similar design [127-129].

Table 3 provides a summary of the sample size calculation for different values of the baseline control rate (50%, 58%), RRR (15%, 20%, 25%, 30%), intra-class correlation coefficient [ICC] (0.05, 0.10) and average cluster size (m) (9,12,15). The primary measure of effect is the difference in the proportions or percentages of patients with cardiovascular hospitalizations and AF-related emergency room visits across study arms over an active study period of 12 months. The criterion for significance (alpha) has been set at 0.05. The test is 2-tailed, which means that an effect in either direction will be interpreted. The statistical power is set at 80%.

The above computation assumes a binomial distribution for the number of patients with cardiovascular hospitalizations and AF-related ED visits, a baseline control rate of about 50% and hypothesized RRR of 20%. We also adjusted the sample size for a potential clustering of patient responses within a practice group, varying the intra-class correlation coefficient (ICC)—which measures the degree of clustering – from 9-15 (see Table 3). Therefore, the required sample size of 1075 patients corresponds to an ICC of 0.05 and average cluster size of m= 9.

P0= the proportion of patients in the control group

MCID=minimal clinically important difference/improvement

P1=proportion in the intervention group

n=Total unadjusted sample size

ICC=intra-cluster/practice correlation coefficient

m=average cluster size

VIF=1+(m-1)ICC=variance inflation factor

n_adj=n*VIF=Total adjusted sample size (adjusted for clustering)

RRR = relative risk reduction

The calculations are based on

CONFIDENTIAL

Control rate of 50% and 58% based on the NS data
RRR varying from 15% to 30%
Average cluster sizes (m) of 20, 25 and 30
ICC values of 0.05 and 0.10
Alpha = 0.05 Beta = 0.20

Table 3. Sample size Calculation

CONFIDENTIAL

P0	RRR	MCID	P1	n	ICC	m	VIF	n_adj	k
0.58	0.3	0.174	0.406	251.0602299	0.05	9	1.4	351.4843218	39.05381354
0.58	0.3	0.174	0.406	251.0602299	0.05	12	1.55	389.1433563	32.42861303
0.58	0.3	0.174	0.406	251.0602299	0.05	15	1.7	426.8023908	28.45349272
0.58	0.25	0.145	0.435	364.9655172	0.05	9	1.4	510.9517241	56.77241379
0.58	0.25	0.145	0.435	364.9655172	0.05	12	1.55	565.6965517	47.14137931
0.58	0.25	0.145	0.435	364.9655172	0.05	15	1.7	620.4413793	41.36275862
0.58	0.2	0.116	0.464	573.6717241	0.05	9	1.4	803.1404138	89.23782375
0.58	0.2	0.116	0.464	573.6717241	0.05	12	1.55	889.1911724	74.09926437
0.58	0.2	0.116	0.464	573.6717241	0.05	15	1.7	975.241931	65.01612874
0.58	0.15	0.087	0.493	1022.444138	0.05	9	1.4	1431.421793	159.0468659
0.58	0.15	0.087	0.493	1022.444138	0.05	12	1.55	1584.788414	132.0657011
0.58	0.15	0.087	0.493	1022.444138	0.05	15	1.7	1738.155034	115.8770023
0.58	0.3	0.174	0.406	251.0602299	0.1	9	1.8	451.9084138	50.21204598
0.58	0.3	0.174	0.406	251.0602299	0.1	12	2.1	527.2264828	43.93554023
0.58	0.3	0.174	0.406	251.0602299	0.1	15	2.4	602.5445517	40.16963678
0.58	0.25	0.145	0.435	364.9655172	0.1	9	1.8	656.937931	72.99310345
0.58	0.25	0.145	0.435	364.9655172	0.1	12	2.1	766.4275862	63.86896552
0.58	0.25	0.145	0.435	364.9655172	0.1	15	2.4	875.9172414	58.39448276
0.58	0.2	0.116	0.464	573.6717241	0.1	9	1.8	1032.609103	114.7343448
0.58	0.2	0.116	0.464	573.6717241	0.1	12	2.1	1204.710621	100.3925517
0.58	0.2	0.116	0.464	573.6717241	0.1	15	2.4	1376.812138	91.78747586
0.58	0.15	0.087	0.493	1022.444138	0.1	9	1.8	1840.399448	204.4888276
0.58	0.15	0.087	0.493	1022.444138	0.05	12	1.55	1584.788414	132.0657011
0.58	0.15	0.087	0.493	1022.444138	0.05	15	1.7	1738.155034	115.8770023
0.5	0.3	0.15	0.35	332.7644444	0.05	9	1.4	465.8702222	51.76335802
0.5	0.3	0.15	0.35	332.7644444	0.05	12	1.55	515.7848889	42.98207407
0.5	0.3	0.15	0.35	332.7644444	0.05	15	1.7	565.6995556	37.7133037
0.5	0.25	0.125	0.375	486.08	0.05	9	1.4	680.512	75.61244444
0.5	0.25	0.125	0.375	486.08	0.05	12	1.55	753.424	62.78533333
0.5	0.25	0.125	0.375	486.08	0.05	15	1.7	826.336	55.08906667
0.5	0.2	0.1	0.4	768.32	0.05	9	1.4	1075.648	119.5164444
0.5	0.2	0.1	0.4	768.32	0.05	12	1.55	1190.896	99.24133333
0.5	0.2	0.1	0.4	768.32	0.05	15	1.7	1306.144	87.07626667
0.5	0.15	0.075	0.425	1378.097778	0.05	9	1.4	1929.336889	214.3707654
0.5	0.15	0.075	0.425	1378.097778	0.05	12	1.55	2136.051556	178.0042963
0.5	0.15	0.075	0.425	1378.097778	0.05	15	1.7	2342.766222	156.1844148
0.5	0.3	0.15	0.35	332.7644444	0.1	9	1.8	598.976	66.55288889
0.5	0.3	0.15	0.35	332.7644444	0.1	12	2.1	698.8053333	58.23377778
0.5	0.3	0.15	0.35	332.7644444	0.1	15	2.4	798.6346667	53.24231111
0.5	0.25	0.125	0.375	486.08	0.1	9	1.8	874.944	97.216
0.5	0.25	0.125	0.375	486.08	0.1	12	2.1	1020.768	85.064
0.5	0.25	0.125	0.375	486.08	0.1	15	2.4	1166.592	77.7728
0.5	0.2	0.1	0.4	768.32	0.1	9	1.8	1382.976	153.664

3.9 Statistical Analysis:

The analysis and reporting of the trial results will follow the CONSORT Statement for cluster-randomization trials [129]. The baseline characteristics of the practices and patients will be reported by group as mean (standard deviation) or median (first quartile, third quartile) for continuous variables, depending on the distribution, and count (percent) for categorical variables. The analysis will follow the intention-to-treat (ITT) principle. The unit of randomization will be the practice. The unit of analysis will be the patient. We will use multiple imputation to handle missing data to enable ITT analysis. Multiple imputation is a Monte Carlo technique in which the missing values are replaced by $m > 1$ simulated versions, where 'm' is typically small. Each of the simulated complete datasets will be analyzed by standard methods, and the results will be combined to produce estimates and confidence intervals that incorporate missing data uncertainty [133]. We will use generalized estimating equations (GEE) – assuming exchangeable correlation structure for patients within the same practice, and adjusting for urban and rural practice types to analyse all outcomes [130]. Unlike ordinary regression techniques, GEE allows us to model the intra-practice correlation among patients within each practice. The results will be reported as the estimate of the effect, corresponding 95% confidence interval and associated p-values. All p-values will be reported to three decimal places with those less than 0.001 reported as $p < 0.001$. The criterion for statistical significance will be set a priori at $\alpha = 0.05$, and adjusted using the Bonferroni method for multiple secondary analyses. All analyses will be performed using SAS 9.4 (Cary, NC).

Sensitivity analyses: 1) There are several methods for analyzing cluster RCTs [131]. Therefore, we will perform sensitivity analyses using some of the commonly used patient-level methods such as random-intercept model and cluster-level (i.e. random- and fixed-effects meta-analytic) methods to assess the robustness of the results. 2) Given that the unit of randomization is the practice, there is a higher chance of potential imbalance of patient-level baseline characteristics. We will perform some sensitivity analysis to adjust for any potential imbalance.

HRQoL

The proportion of patients with reported impairment in each of the five EQ-5D-5L dimensions will be calculated for each arm. Health utilities will be calculated using the Canadian EQ-5D-5L scoring algorithm. QALYs accumulated over the study period will be calculated using the area under the curve method.

Costs

Total cost will be calculated using the sum of the product of resource utilization items (e.g. length of hospital stay, medications) and corresponding unit costs.

Cost effectiveness

The incremental cost effectiveness ratio (ICER) will be calculated by dividing the incremental difference in the mean cost between the treatment arms by the incremental difference in the mean QALYs between the arms. Sampling uncertainty is a critical issue that needs to be sufficiently and adequately dealt with in any economic evaluation alongside a clinical trial.

CONFIDENTIAL

Nonparametric bootstrap with replacement will be used to estimate the confidence intervals around the ICER. The decision uncertainty will be presented using the cost effectiveness acceptability curves in which maximum willingness to pay value from the policy maker's perspective is explicitly considered. Both base case and uncertainty analyses will be stratified by demographic and socioeconomic variables (such as age, gender and income). These stratified analyses are important for any economic evaluation to identify subpopulations that could potentially receive the most benefit from the intervention.

